3.3 Patient Data and Study Conduct

3.3.1 Patient Disposition

Counts and percentages of patients who were transitioned to oral dose, discontinued early from the study, and completed the study will be summarized by treatment/dose group and overall for the SAF. Reasons for early discontinuation will also be summarized. An associated patient-level listing will be provided.

3.3.2 Protocol Deviations

Protocol deviations will be identified based on the clinical data as defined in the Protocol Deviation Plan. The Protocol Deviation Plan will define all protocol deviations as either CSR reportable or non-CSR reportable deviations. Counts and percentages of participants with CSR reportable protocol deviations by deviation category will be summarized by treatment/dose group and overall for the SAF. A listing of CSR-reportable protocol deviations will be generated.

3.3.3 Demographic and Baseline Characteristics

Demographic and baseline characteristics outlined below will be summarized with descriptive statistics or counts and percentages of patients as appropriate by treatment/dose group and overall for the SAF.

- Age
- Sex
- Race
- Weight at baseline
- Height at baseline
- Body mass index (BMI) at baseline.

An associated patient-level listing will also be provided.

3.3.4 Concomitant Medications

Concomitant medications will be coded to anatomical therapeutic chemical (ATC) class and preferred term using the World Health Organization (WHO) Drug Dictionary Mar 2018 Global B3. For summary purposes, medications will be considered prior medications if they stopped prior to the first dose of study drug and concomitant medications if they were taken at any time after the first dose of study drug (i.e., started prior to the first dose of study drug and were ongoing or started after the first dose of study drug). Concomitant medications for IV dosing period are defined as medications that were taken any time after the first IV dose and prior to first oral dose. Concomitant medications for oral dosing period are defined as medications that were taken any time after the first oral dose. Based on this definition, the same concomitant medication can be taken in both IV dosing period and oral dosing period.

If a medication has incomplete start or stop dates, dates will be imputed to determine whether a medication should be considered prior or concomitant. Details on the imputation of incomplete dates will be provided in the final SAP to reflect CRF design and instructions.

Counts and percentages of patients taking concomitant medications by ATC class and preferred term will be summarized by IV dosing period, oral dosing period and in total based on the Safety Set. A patient-level listing of all concomitant medications will also be provided.

3.3.5 Study Drug Exposure

Days of exposure to study drug will be calculated as:

(date of last dose of study drug – date of first dose of study drug + 1).

Details regarding the last oral dose date imputation are as follows:

- For patients who filled out form Date of Visit and did not continue to next yearly visit or completed all yearly visits for oral study drug, last oral dose date will not be imputed. The last oral dose date recorded in the raw data will be used.
- For patients who completed the study or discontinued early from study prior to Jan 1, 2022, last oral dose date will not be imputed. The last oral dose date recorded in the raw data will be used.
- For patients who finished Date of Visit form at the follow-up visit, the date of follow-up (FU) visit will be compared to the date of oral doses recorded.
 - If date of FU visit > last oral dose date record + 1 year, then last oral dose date will be imputed as (last oral dose date recorded + 365).
 - If date of FU visit ≤ last oral dose date record + 1 year, then last oral dose date will be imputed as (FU visit date - 1).
- For all other patients, last oral dose date will be imputed as Feb 1, 2023.

Note that the exposure calculation is intended to describe the length of time a patient was exposed to study drug and therefore does not take study drug interruptions into account. Days of exposure to study drug will be summarized overall based on the SAF for both IV and oral administration.

Study drug exposure will be also presented in a patient-level listing.

3.4 Endpoint Assessment

The SAF will be the primary population for the efficacy analyses. Efficacy data will also be analyzed using the PP as supportive analyses for selected endpoints.

3.4.1 Primary Endpoints

The primary endpoints (Safety measures) are as follows:

- Incidence and severity of treatment-emergent adverse events (TEAEs),
- Incidence and severity of abnormal clinical laboratory test results (hematology, chemistry),
- Incidence of abnormal physical examination results,
- Incidence of abnormal vital sign values (blood pressure [BP] and pulse rate [PR]), and
- Incidence of abnormal 12-lead electrocardiogram (ECG) results or values.

3.4.2 Secondary Endpoints

The secondary endpoints (Efficacy measures) of the study are:

- 6-minute walk test score (6MWT),
- Patient global assessment score (based on the KCCQ instrument),
- Physician's Assessment of Functional Class (measured by NYHA Functional Class assessment), and
- Incidence of clinical events (death and hospitalizations).

All Secondary Endpoint measurements will be presented in patient-level listings.

3.4.3 Subgroup Analyses

No subgroup analyses will be performed for this study.

3.5 Primary Endpoint Assessment

Primary endpoint safety measures will be summarized by treatment/dose group and overall using descriptive statistics (number of observations, mean, median, standard deviation, minimum, maximum) for continuous variables and counts and percentages for categorical data. Summaries will be based on the SAF. Associated patient-level listings will also be provided for the primary endpoint safety measures. Primary endpoint efficacy measures will not be summarized but will be provided in patient-level listings.

3.5.1 Adverse Events (AEs)

Adverse events will be coded according to the MedDRA guidance version 21.0. An adverse event is considered treatment-emergent if the start date/time of the event is:

- On or after the date/time of first IV dose for IV dosing only patients and patients who transitioned to oral dosing and were in IV period,
- On or after the date/time of first oral dose for patients who transitioned to oral dosing and were in oral period.

An overview of AEs will be provided including counts and percentages of patients with the following:

- Any TEAEs (overall and by maximum severity)
- Any study drug-related TEAEs
- Any serious TEAEs (TESAEs)
- Any TEAEs leading to discontinuation of study drug
- Any TEAEs leading to discontinuation of study.

Counts and percentages of patients will also be presented by system organ class and preferred term for each of the categories in the overview. TEAEs and TESAEs will be also provided in patient-level listings.

If an adverse event has incomplete start or stop dates, dates will be imputed to determine whether the adverse event was treatment-emergent. Details on the imputation for incomplete dates will be provided in the final SAP to correspond to CRF design and instructions. Summaries will be performed by treatment/dose group.

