7.4 Non-successful transition to oral levosimendan

Patients who do not successfully transition to oral levosimendan may re-start IV levosimendan, within a minimum of 7 days from their last dose of oral levosimendan. Once a patient re-starts IV levosimendan, they will continue to receive study drug based on the original date of entry into the TNX-LVO-05 study (i.e., final visit in the parent study, TNX-LVO-04) return to their weekly IV levosimendan dose regimen they were on prior to starting the oral transition.

Patients that re-start IV levosimendan will not have the opportunity to be given oral levosimendan in the future.

The starting dose of IV levosimendan should be at the same rate the patient was receiving prior to the transition to oral levosimendan. After re-starting IV levosimendan, the patient should be contacted by telephone after 2 weeks to assess for any safety events.

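### The SAP's IV and oral period rules do not cover patients who return to IV after a failed oral transition, so their medications, adverse events and exposure are misassigned or unassigned

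*SAP*

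**What the plan says.** Protocol 7.4 provides for a return to infusions: "Patients who do not successfully transition to oral levosimendan may re-start IV levosimendan, within a minimum of 7 days", counted from the last oral dose. It then rules out a second oral course: "Patients that re-start IV levosimendan will not have the opportunity to be given oral levosimendan in the future". The longest sequence the protocol allows is therefore IV, oral, IV, with one oral interval.

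The SAP does not mention this path. Section 2.2.3 describes patients who enter on IV, some of whom move to oral. Section 3.2.1 has patients analysed by the dose they received and splits the summaries into IV period, oral period and total. Three rules put that split into effect:

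- **Concomitant medications (3.3.4).** The IV period covers "medications that were taken any time after the first IV dose and prior to first oral dose". For oral: "Concomitant medications for oral dosing period are defined as medications that were taken any time after the first oral dose".
- **Adverse events (3.5.1).** The IV rule, tied to being in the IV period, opens "On or after the date/time of first IV dose for IV dosing only patients and patients who transitioned to oral dosing and were in IV". The oral rule reads "On or after the date/time of first oral dose for patients who transitioned to oral dosing and were in oral period". Neither period is given a stop date.
- **Exposure (3.3.5).** Days are last dose date minus first dose date plus 1, a calculation that "therefore does not take study drug interruptions into account". Exposure is reported for both routes, in Tables 14.1.4.1 (IV) and 14.1.4.2 (oral). Several branches impute the last oral dose date, and none mentions patients who are back on IV.

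**The concern.** Safety is the primary objective, and the route split is how the SAP presents it. Restarters are by definition the patients in whom the oral switch did not work, so errors in placing their data are not random with respect to route. Protocol 1.1 gives avoidance of IV-line infection as a reason for the switch. A line infection after infusions resume, if shown in the oral column, would blur the contrast that readers will look for.

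The exposure tables are the natural denominators for the event tables. If a restarter's IV exposure absorbs the oral interval while oral exposure counts it again, the two routes add to more days than the patient was in the study.

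**Working it through.** The documents state no figure on this point, so there is none to reproduce. The check applies the SAP's rules to an IV-oral-IV patient.

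**Inputs from the documents**
- IV treatment ends two years after entry (Protocol 1.1 and 7.4): taken as day 730.
- First oral dose 7 to 9 days after the final infusion (Time and Events Schedule, footnote 3): 7 used.
- Transition lasts 6 weeks, with a Week 8 visit for some patients (Protocol 7.1): 42 and 56 oral days, with 14 added for an early failure.
- Restart at least 7 days after the last oral dose (Protocol 7.4): 7 used.

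**Assumed:** first IV dose on day 1; last infusion before the switch on day 365 (180 and 540 also tried); last infusion on day 730.

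**Timeline, 42 oral days**
- First oral dose: 365 + 7 = day 372
- Last oral dose: 372 + 42 − 1 = day 413
- IV restart: 413 + 7 = day 420

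**(a) Medications.** SAP 3.3.4 closes the IV period at day 372 and never closes the oral period. A drug started on day 500, during weekly infusions, is tabulated as oral and not as IV. This follows from the stated rule.

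**(b) Adverse events.** SAP 3.5.1 requires the patient to be in the oral or the IV period at the time, but dates neither for a restarter. Two readings are open:
- Carry over the 3.3.4 boundary. The oral window is then 730 − 372 + 1 = 359 days, of which 730 − 420 + 1 = 311 (87%) fall on or after the IV restart. Across the nine combinations of switch day (180, 365, 540) and oral duration (14, 42, 56 days), the share is 66% to 96%.
- Follow the dose-received principle in 3.2.1. Events from day 420 then go to IV.

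Two programmers could produce different tables and each cite the SAP.

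**(c) Exposure, applied by route**
- IV by formula: 730 − 1 + 1 = 730 days
- IV by segment: 365 + 311 = 676 days
- Excess: 730 − 676 = 54 days, made up of 42 oral days and two 6-day gaps (days 366–371 and 414–419)
- Oral by formula on recorded dates: 413 − 372 + 1 = 42 days
- IV plus oral: 730 + 42 = 772 days against 730 calendar days

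| Oral days | IV by formula | IV by segment | Excess |
|---|---|---|---|
| 14 | 730 | 704 | 26 |
| 42 | 730 | 676 | 54 |
| 56 | 730 | 662 | 68 |

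The excess is the oral days plus 12 gap days, whichever switch day is used.

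**Imputation.** If this patient fell into the follow-up-visit branch, with that visit assumed on day 731, then 731 is not later than 413 + 365 = 778. The last oral dose would be imputed as 731 − 1 = day 730, and oral exposure would be 730 − 372 + 1 = 359 days instead of 42. Which branch applies depends on the forms completed and on calendar dates.

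**Effect on incidence.** The parent study randomised 37 patients (Protocol 1.3.5), so the oral denominator cannot exceed 37. One misassigned patient moves an oral incidence by at most 1/N: 1/37 = 2.7 points, or 1/20 = 5 points if N were 20 (assumed).

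**The case against.** The strongest reply is that the adverse event rule does not say what a quick reading suggests. A reader might infer that every event after the first oral dose is counted as oral. The rule also requires the patient to be in the oral period, the open-ended boundary is written only for medications, and 3.2.1 points to the dose received. A failed transition might not even count as having transitioned. This stands: for events the defect is a missing definition, not an explicit misassignment.

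Other stronger readings also fail:
- *The oral interval is double counted for everyone who switched.* For a patient who stays on oral, IV exposure ends at the last infusion. Only restarters are affected, and only if the formula is applied by route. Its wording says only study drug; the two route-specific tables make the by-route reading the natural one.
- *Every safety table is affected.* Laboratory, vital sign, ECG and physical examination data appear only as listings.
- *One patient shifts an incidence by at least 1/N.* The tables count patients, so a restarter who already had the same event during true oral dosing shifts it by zero.
- *A 30-day window after the last dose must be imposed on all events.* Protocol 9.1 and 9.2.4 already limit collection, so this is a preference.

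It can also be said that no hypothesis is tested, that patient listings allow restarters to be traced, and that ignoring interruptions is a declared choice. These points lessen the consequences but supply no rule. A whole course on the other route is also more than an interruption. Finally, SAP section 4 refers to protocol v5.0, while the protocol reviewed is v4.1, and programming specifications are held separately. Either could bear on the point, and neither could be checked.

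**Conclusion.** The concern holds for patients who return to IV, and only for them. Medication assignment after restart is wrong by a stated rule. Adverse event attribution after restart is undefined, and the one boundary the SAP does define would send those events to oral, against its own dose-received principle. IV exposure applied by route is overstated by the oral interval plus the gaps, and oral exposure may be overstated by imputation.

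The affected outputs are the period-split adverse event and concomitant medication tables and the two exposure tables. The overall size cannot be stated because the documents do not say how many patients restarted; if none did, the effect is nil. The day counts are illustrations that rest on the assumed dates. The incidence figures are upper limits per misassigned patient. With so few patients, one or two restarters would be visible in the tables, so the rule should be settled before database lock and not after the events have been seen.

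**What to change.** In SAP 3.3.4, 3.3.5 and 3.5.1, replace the single boundary with three dated segments:

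- **IV-1:** first IV dose to the day before the first oral dose.
- **Oral:** first oral dose to the day before any IV restart.
- **IV-2:** from the IV restart onward.

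Assign adverse events by onset date; gap days between the last oral dose and the restart then belong to Oral. Assign medications to each segment in which they were used. Compute exposure by route as the sum of segment lengths, using the actual first and last dose dates within each segment, so that gap days are not counted as exposure. Exempt restarters from the last-oral-dose imputation. State whether IV-2 is pooled with IV or shown in its own column, and add a listing of restarters with their switch dates.

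The cost is SAP wording, one derived period flag and one short listing. No new data are needed. Sections 3.3.4 and 3.5.1 already defer date-imputation details to a final SAP, so the change can go in at the same time.

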2.2 Study Objectives

2.2.1 Primary Objectives

This study will evaluate the safety and tolerability of levosimendan in extended use after completion of the parent study.

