5.5.2 Dose Adjustment

The oral levosimendan dose may be decreased in 1 mg increments or interrupted as clinically warranted if the subject has hypotension, tachycardia, or signs or symptoms consistent with hypovolemia (e.g., low SBP, decreasing urine output with rising blood urea nitrogen [BUN] and serum creatinine). Record the date of discontinuation or down titration. Patients should be monitored closely until clinically stable.

Missed doses should be skipped and not taken as a double dose at the next dosing time.

Refer to the following subsections for additional guidance on events that require study drug discontinuation or dosage adjustment, permanent discontinuation, and re-initiating study drug in subjects in whom clinical stability has been restored.

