14.3 ATTACHMENT 3: Cardiac Event Recommendations and Management

Changes in BP or HR that could represent a significant safety concern should be reported to the treating physician.

If the subject meets any of the dose-limiting event criteria, the following actions on study drug should be undertaken:

1. Blood pressure (systolic) management
 - a. Minimum allowed BP 100 mmHg systolic
 - i. If <120 on antihypertensive meds, recommend reduce or discontinue
 - ii. If >120 on antihypertensive meds, no change.
2. Low blood pressure (systolic <100) management **without symptoms**
 - a. On diuretics
 - i. With edema = no change
 - ii. No edema = reduce or withdraw
 - b. On antihypertensive meds
 - i. Reduce/withdraw
 - c. On no diuretics or antihypertensive meds
 - i. No symptoms = observe
 - ii. BP <90 = reduce levosimendan dose
3. **Symptomatic** low BP management
 - a. Follow recommendations of asymptomatic scenario (above), **and**
 - i. BP <100 mild symptoms = levosimendan dose reduction
 - ii. BP <100 severe symptoms = IV phenylephrine and levosimendan dose reduction
 - iii. BP <90 on lowest dose = discontinue study
4. Sinus tachycardia at rest
 - a. HR >110 = repeat three times per protocol and obtain BP to validate
 - b. HR >110 without symptoms = in the absence of hypotension (above), observe
 - c. HR >110 with symptoms of worsening dyspnea in the absence of hypotension (above) = levosimendan dose reduction
 - d. HR >120 (validated) without symptoms = obtain ECG to determine if sinus tachycardia or atrial-fibrillation. *(If HR > 120, the treating physician should be contacted.)*
 - i. If sinus tachycardia = levosimendan dose reduction or withdraw
 - ii. If atrial fibrillation = heart rate drug management
 - e. Persistent HR >120 despite any/all above measures = discontinue study

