2.1.1 Primary Objectives

The primary objectives are to evaluate the safety and tolerability of levosimendan in extended use after completion of the parent study.

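### Tolerability is a primary objective, but no planned summary table shows dose reductions, interruptions, dose level by visit or returns to IV

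*SAP*

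**What the plan says.** **Objective.** Protocol 2.2.1: "This study will evaluate the safety and tolerability of levosimendan in extended use after completion of the parent study". SAP 2.1.1: "The primary objectives are to evaluate the safety and tolerability of levosimendan in extended use after completion of the parent study".

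**How the protocol handles a dose that is not tolerated.** Oral dose steps depend on tolerability (1.3.8.3). The footnote to the titration table in 5.5.1 sends patients who do not tolerate the three-times-daily step down one step. Section 2.5 gives down-titration or discontinuation as the responses to safety concerns. Sections 5.4.2 (IV) and 5.5.2 (oral) allow reduction or interruption for hypotension, tachycardia or signs of hypovolemia. Attachment 3 names levosimendan reduction in several places, for example "BP <100 mild symptoms = levosimendan dose reduction". Section 7.4 lets patients whose oral transition fails go back to IV.

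**What is recorded.** Protocol 5.5.2: "Record the date of discontinuation or down titration"; section 5.4.2 asks for the time in the same way. Section 9.1.5 has dose adjustment for study-specific events of interest captured in the eCRF. The patient diary (2.3 and Attachment 5) records the capsules taken each day.

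**What the SAP tabulates.** The overview in 3.5.1 has five categories: any TEAE (overall and by maximum severity), drug-related TEAEs, serious TEAEs, "Any TEAEs leading to discontinuation of study drug", and "Any TEAEs leading to discontinuation of study". Each is repeated by system organ class and preferred term. Exposure (3.3.5) is days from first to last dose, with interruptions disregarded. Disposition (3.3.1) counts patients transitioned, discontinued early and completed.

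**The concern.** In a regimen titrated to tolerability, an event that forces a lower dose or a pause is itself a tolerability result. The SAP reports what happened to treatment after an event only when the drug or the study was stopped. If most dose-limiting events are managed short of stopping, the summaries will not separate a patient who held the intended dose from one who had to be reduced, paused or returned to IV.

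The study is descriptive, with no hypothesis test (SAP 3.1.5). The summary tables are therefore its main result on tolerability, and a gap in them is a gap in the answer to a primary objective.

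**Working it through.** No formula applies. The check sets the protocol's ways of handling intolerance against the SAP's list of tables and listings.

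**Count of outputs.** The list holds 13 tables: six on disposition, deviations, demographics, exposure (two) and concomitant medication (14.1.1 to 14.1.5); one AE overview (14.3.1); and six AE tables (14.3.2.1 to 14.3.2.6). There are 16 listings.

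| Handling in the protocol | Where | Summary table that shows it |
|---|---|---|
| Discontinuation | 2.5, 3.4.1, Attachment 3 | 14.1.1, 14.3.1, 14.3.2.5, 14.3.2.6 |
| Dose reduction | 2.5, 5.4.2, 5.5.1, 5.5.2, Attachment 3 | none |
| Interruption | 5.4.2, 5.5.2 | none; exposure disregards it |
| Return to IV after failed transition | 7.4 | none named |
| Dose level by visit | 10.6 | none |

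**How prominent reduction is.** In Attachment 3, five lines name levosimendan reduction (2.c.ii, 3.a.i, 3.a.ii, 4.c and 4.d.i, the last also allowing withdrawal). Two lines call for discontinuing the study (3.a.iii and 4.e), one at the lowest dose and one after other measures have failed. Other lines call for observation, changes to diuretics or antihypertensives, or rate control.

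**Whether other outputs fill the gap.**
- *TEAE incidence and severity.* Protocol 9.1.1 grades severity by effect on daily activities and clinical status and by need for treatment, not by effect on the dose. Two hypotension events of equal severity count alike, even if one forced a reduction and the other changed nothing.
- *Reductions with no AE.* Attachment 3 item 2.c.ii calls for a reduction on a blood pressure value under the heading for patients without symptoms. Under protocol 8.1.2.4 a vital-sign deviation becomes an AE only if the investigator judges it clinically significant. Without a recorded AE, such a patient enters no AE table on that account, and vital signs are only listed (SAP 3.5.3).
- *Grouping.* SAP 3.2.1 summarises by IV period, oral period and total. The treatment/dose group used elsewhere is not defined more finely, so the grouping does not reveal oral dose level.
- *Return to IV.* The SAP does not say whether going back to IV counts as discontinuing study drug.
- *Listings.* Dose changes could appear in Listing 16.2.4.2 (exposure), but its columns are not specified.

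**Comparison with the protocol's own analysis section.** Protocol 10.6 promises the number of subjects receiving each dose, by visit. No listed table delivers it. SAP section 4 states agreement with protocol v5.0, while the protocol available is v4.1, so a later change to 10.6 cannot be ruled out.

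**Size.** The parent study randomised 37 patients (protocol 1.3.5), but neither document says how many rolled over, how many moved to oral dosing, or what rate of reduction is expected. No percentage follows from these.

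**The case against.** The strongest reply is that tolerability is already covered. A reader might infer that the SAP measures it through discontinuations alone, and that is wrong. Incidence, maximum severity, relatedness and seriousness of TEAEs are all tabulated, and discontinuation is two of the five overview categories. A reader might also infer that a down-titrated patient is presented as tolerating the drug. No output has a tolerated category, and a patient reduced for a recorded event still counts under that preferred term. The event is visible; what is lost is that it limited the dose.

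Nor is down-titration the only response. Attachment 3 also lists observation and changes to other drugs, and section 2.5 allows discontinuation at the physician's discretion.

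Protocol 10.8 asks for AEs leading to withdrawal, not AEs leading to reduction, so on that row the SAP follows the protocol and the addition is an improvement, not the repair of a departure.

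Finally, the case report form is not available. Section 9.1.5 covers events of interest, and section 9.2.6 mentions action taken with the product only for SAEs resulting in death and events ongoing at death. An action-taken field for every TEAE is therefore an assumption.

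All of this stands and narrows the point. It does not supply a table on reductions, interruptions, dose reached or failed transitions. The uncertainty about the form is a reason to count from dosing records as well as from AE records.

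**Conclusion.** The point holds as a gap in reporting. The SAP tabulates TEAE incidence, severity, relatedness, seriousness and discontinuations, but none of its 13 tables covers dose reduction, interruption, dose level by visit or return to IV. Dose-limiting intolerance managed without discontinuation cannot be identified in any summary table, and a reduction with no recorded AE may appear in none.

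The documents do not support the stronger claim that the plan would report intolerant patients as tolerant. They also give no basis for saying how far any rate would be understated.

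The conclusion assumes that the SAP's list of tables is complete and that the unspecified listing columns are no substitute for a summary. The missing AE rows do not depend on the protocol version. The mismatch with section 10.6 is established only against v4.1.

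**What to change.** Before database lock, add to the SAP:

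1. In Table 14.3.1, by IV and oral period and in total, rows for TEAEs leading to dose reduction and TEAEs leading to interruption, with a matching SOC/PT table. Use the dose-adjustment or action-taken data on the eCRF where collected, and state in a footnote which events that covers.
2. From the dosing records, and so not dependent on an AE having been recorded, counts of patients down-titrated, interrupted, or returned to IV after a failed oral transition. State whether a return to IV also counts as discontinuation of study drug.
3. The number of subjects receiving each dose by visit, as in protocol 10.6. If v5.0 removed that summary, say so in SAP section 4.

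The cost is a few extra rows and tables built on dose information that the protocol already asks sites to record, plus a check of what the eCRF holds. The resulting picture of tolerability may look less favourable. No dosing or management rule is affected.
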